To assess the pharmacokinetics (PK) of peposertib	Pharmacokinetic profile of peposertib in terms of PK parameter estimates (e.g. C_{max} , AUC_{0-t} , t_{max} , CL/f , Vz/f , and $t_{1/2}$)	Fraction day (FD)1 and FD9

Overall Design: This is a multicenter, open-label, single arm, dose escalation study in participants with locally advanced rectal cancer.

The study will consist of a Screening period of 4 weeks, a Treatment period of 5 to 5.5 weeks (25 or 28 FD) (DLT period), a Short-term Safety Follow-up period of 13.5 weeks (including 30 days after surgery), a Long-term Safety Follow-up period until 1 year after the start of study intervention/randomization.

Number of Participants: The planned cohort size is 3 participants. The total sample size will depend on the number of cohorts to be evaluated. It is anticipated that 18 to 30 evaluable participants will be required.

Study Intervention Groups and Duration: Participants will be assigned to peposertib given in combination with capecitabine 825 mg/m² twice daily 5 days/week and RT of 50 to 50.4 Gy to the tumor area and 45 Gy to the electively irradiated tissues in 25 or 28 fractions (corresponding to 5 to 5.5 weeks). The starting dose of peposertib for the first cohort will be 50 mg once daily 5 days/week. The peposertib dose for the next cohorts will be determined by the Safety Monitoring Committee (SMC) guided by a Bayesian 2-parameter logistic regression model with overdose control.

[figure not shown]
Premature Discontinuation: As of 06 May 2021, in the Phase Ib dose escalation part, 19 participants have been treated with doses ranging from 50 to 250 mg peposertib once daily plus capecitabine and RT. Preliminary clinical data from 16 participants that have finished the study up to Week 19 as well as changing treatment landscape in locally advanced rectal cancer indicate that the ability to generate a meaningful proof of concept under the current protocol is low. Therefore, the dose escalation in the Phase Ib part will be prematurely discontinued after completing the Cohort 5 of 150 mg, and the Phase II part of the study will not be initiated.

Involvement of Special Committee(s): Yes

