In conclusion, emerging clinical safety data from studies EMR100036-001 and EMR100036-002, and supportive results of a comprehensive series of nonclinical safety pharmacology, PK, and toxicology studies, as well as primary and secondary PD findings support continued clinical development of peposertib in combination with RT, and/or chemotherapy.

3 Objectives and Endpoints

Study objectives and endpoints are provided in [Table 6](#). Statistical analysis of the endpoints is described in [Section 9.4](#).

Table 6 Study Objectives and Endpoints

Objectives	Endpoints (Outcome Measures)	Endpoints (Outcome Measures) Timeframe
Primary		
To define an MTD and RP2D of peposertib in combination with capecitabine and RT	Occurrence of dose limiting toxicities	Time from first study intervention to the end of CRT with a final assessment at 4 weeks after surgery
Secondary		
To evaluate safety and tolerability of peposertib in combination with capecitabine and RT	
 • Occurrence of TEAEs and treatment-related adverse events according to the NCI-CTCAE version 5.0 • Occurrence of abnormalities (Grade ≥ 3) in laboratory test values, markedly abnormal vital sign measurements, and clinically significantly abnormal ECGs including clinically important increases in QT interval (QTcF) 	Time from first study intervention to final assessment at 1 year
To explore antitumor activity of peposertib in combination with capecitabine and RT	
 • Composite endpoint of pCR/cCR • Disease-free Survival • pCR • cCR • Local recurrence and/or distant metastasis • Neoadjuvant rectal score 	
 • Pathology evaluation of specimen after surgery (pCR) and clinical evaluation 1 to 2 weeks prior to surgery (cCR) • Time from first study intervention to final assessment at 1 year • Pathology evaluation of specimen after surgery • Time from first study Intervention until clinical evaluation 1 to 2 weeks prior to surgery • Time from surgery to final assessment at 1 year • Pathology evaluation of specimen after surgery
To assess the PK of peposertib	PK profile of peposertib in terms of PK parameter estimates (e.g. C _{max} , AUC _{0-t} , t _{max} , CL/f, Vz/f, t _{1/2})	FD1 and FD9

CCI

cCR=Clinical Complete Response, CRT=chemoradiotherapy, CCI [REDACTED]
[REDACTED] ECG=electrocardiogram, FD=fraction day, MTD=maximum tolerated dose, NCI-CTCAE=National Cancer

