4.1.3 Follow-up Periods

The study follow-up will include:

- **Short-term Safety Follow-up:** the duration of the Short-term Safety Follow-up is approximately 13.5 to 14 weeks after treatment completion, including 30 days after surgery, with an optional 1 visit per week from Week 7 to Week 14 in case of acute toxicities until recovery to Grade 1 or to baseline. For all participants, a mandatory visit will be performed at Week 14, approximately 1 to 2 weeks prior to surgery, including a tumor assessment with MRI (T_2 weighted and diffusion weighted) needed for restaging and evaluation. Additional details on tumor evaluation methods and response assessments are provided in Section 8.1.2.
- Surgical intervention must be performed 15 weeks (\pm 14 days) after start of study intervention/randomization (i.e. approximately 9.5 weeks after stopping RT), unless there are contraindications for surgery, or if the participant refuses. The last Short-term Safety Follow-up visit is scheduled for Week 19, approximately 4 to 6 weeks after surgical intervention/imaging/biopsy, as per SoC. During this visit, all safety information since the last visit, including surgical and/or biopsy morbidities/toxicities will be collected.
- **Long-term Safety Follow-up:** participants will be followed-up at 21 and 27 weeks after start of study intervention/randomization; every 3 months until 1 year after start of study intervention/randomization. Details on tumor evaluation methods and response assessments are provided in Section 8.1.2. Adjuvant chemotherapy is allowed as per local standards (see Section 6.5). Participants receiving adjuvant chemotherapy will continue to follow the schedule of activities (SoA) as per protocol. If adjuvant chemotherapy is given, any additional safety evaluations/laboratory tests will be as per local practice.
- Participants who have already been followed up for more than 1 year (Long-term Safety or Survival Follow-up) will be discontinued from the study after the approval of protocol amendment version 4.0 by the respective Health Authority and Ethics Boards. Participants will be informed of the discontinuation by the Investigator via a phone call. No further study visits or assessments are planned.

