PR	Partial response
PT	Preferred term
PTV	Planning target volume
PK	Pharmacokinetics
Q1	First quartile
Q3	Third quartile
QTc	Corrected QT interval
QTcF	Fridericia-corrected QT interval
R _{acc}	Accumulation factor
RP2D	Recommended phase 2 dose
RT	Radiotherapy
SAE	Serious adverse event
SAF	Safety analysis population
SD	Stable disease
Sd	Standard deviation
SDTM	Study data tabulation model
SMC	Safety monitoring committee
SOC	System organ class
TEAE	Treatment-emergent adverse event
t _{1/2}	Apparent terminal half-life
t _{max}	Time to reach maximum observed concentration
UCL	Upper confidence limit
ULN	Upper limit of normal
UNK	Unknown
V _{z/f}	Apparent volume of distribution at steady state
WHO-DD	World Health Organization Drug Dictionary
λ _z	Terminal elimination rate constant

3**Modification History**

Unique Identifier for Version	Date of IAP Version	Author	Changes from the Previous Version
1.0	11 February 2020	PPD	NA
2.0	22 March 2021	PPD	
 - Updated author/reviewer list - Update protocol version with V3.0: 
 • addition TNM classification, MRI-EMVI score and MRI-CRM score on Disease History description • addition TNM classification, MRI-EMVI score and MRI-CRM score on tumor evaluation • addition of prior induction therapies description) - Addition of Actual daily Dose PTV1 and PTV2 in radiotherapy cumulative dose calculation - Add analysis to assess COVID-19 impact on the study. - Removed objective “To characterize exposure response (exposure/safety and exposure/efficacy) for M3814 with respect to selected safety and efficacy endpoints” as it is planned only for Phase I and II combined - TEAE leading to a delay in dose time of RT (corresponding to AEs with action taken = “Dose time delayed”) removed from the Adverse Events Leading to Study Intervention Discontinuation description
3.0		PPD	
 - Update protocol version to V4.0 - Long-term Safety Follow-up period shortened to 1 year (previously 2 years) and removed Survival Follow-up. - Removed the endpoints of “overall survival” and “best overall response”. - Added endpoint of “neoadjuvant rectal score”. - Change date added on AE listing

4**Purpose of the Integrated Analysis Plan**

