The purpose of this integrated analysis plan (IAP) is to document technical and detailed specifications for all analyses of data collected for the Phase Ib (dose escalation) protocol MS100036-0020. Results of the analyses described in this IAP will be included in the clinical study report (CSR). Additionally, the planned analyses identified in this IAP may be included in regulatory submissions or future manuscripts. Any post hoc, or unplanned analyses performed to

provide results for inclusion in the CSR but not identified in this prospective IAP will be clearly identified in the CSR.

The IAP is based on Section 9 (Statistical considerations) of the study protocol and protocol amendments and is prepared in compliance with International Conference on Harmonization (ICH) guideline E9.

Separate IAPs will document technical and detailed specifications for the analyses to be provided for safety monitoring committee (SMC) meetings.

Peposertib instead of peposertib (M3814) will be used in the current document.

5 Objectives and Endpoints

Objectives	Endpoints (Outcome Measures)	Endpoints (Outcome Measures) Timeframe	IAP section
Primary			
To define an MTD and RP2D of peposertib in combination with capecitabine and RT	Occurrence of dose limiting toxicities (DLT)	Time from first study intervention to end of chemoradiotherapy with a final assessment at 4 weeks after surgery	15. Safety Analyses
Secondary			
To evaluate safety and tolerability of peposertib in combination with capecitabine and RT	Occurrence of TEAEs and treatment-related adverse-events according to the NCI-CTCAE version 5.0 Occurrence of abnormalities (Grade ≥ 3) in laboratory test values, markedly abnormal vital sign measurements, and clinically significantly abnormal ECGs including clinically important increases in QT interval (QTcF)	Time from first study intervention to final assessment at 5 years	15. Safety Analyses
To explore antitumor activity of peposertib in combination with capecitabine and RT	Composite endpoint of pCR/cCR	Pathology evaluation of specimen after surgery (pCR) and clinical evaluation 1 to 2 weeks prior to surgery (cCR)	14. Efficacy Analyses

Objectives	Endpoints (Outcome Measures)	Endpoints (Outcome Measures) Timeframe	IAP section
	Disease-free Survival	Time from first study intervention to final assessment at 5 years	
	pCR	Pathology evaluation of specimen after surgery	
	cCR	Time from first study intervention until clinical evaluation 1 to 2 weeks prior to surgery	

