	Local recurrence and/or distant metastasis	Time from surgery to final assessment at 5 years	
	Neoadjuvant rectal score	Pathology evaluation of specimen after surgery	
To assess the Pharmacokinetics (PK) of peposertib	PK profile of peposertib in terms of PK parameter estimates (eg, C_{max} , AUC, t_{max} , CL/f Vz/f , $t_{1/2}$)	Fraction Day (FD) 1 and FD9	16.1 Pharmacokinetics
CCI			

CCI

AUC = area under the concentration time-curve ; cCR = clinical complete response; CL/f = apparent total body clearance; C_{\max} = maximum observed plasma concentration; CCI [REDACTED]; DLT = dose limiting toxicity; ECG = electrocardiogram; FD = fraction day; MTD = maximum tolerated dose; NCI-CTCAE = National Cancer Institute – Common Terminology Criteria for Adverse Events; pCR = pathological complete response; CCI [REDACTED] PK = pharmacokinetics; QTcF = fridericia-corrected QT interval; RP2D = recommended phase 2 dose; RT = radiotherapy; TEAE = treatment emergent adverse event; $t_{1/2}$ = apparent terminal half-life; t_{\max} = time to reach maximum observed concentration; V_z/f = apparent volume of distribution at steady state.

6 Overview of Planned Analyses

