6.4 Further Analyses

Follow-up analyses to report further efficacy and safety data will be done once all participants have completed the 1-year follow-up period and at the end of study.

Additional analyses of safety and preliminary antitumor activity might be performed for the purpose of publication at scientific congresses.

7 Changes to the Planned Analyses in the Clinical Study Protocol

Outcome of the tumor assessment prior to surgery is reflected in the analysis of cCR. As the number of subjects in the dose escalation cohorts is low, PK exposure of peosertib versus safety and exposure will not be performed.

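### SAP Section 5 keeps 5-year windows for safety, DFS and recurrence where the protocol ends them at 1 year, and no SAP rule stops counting at 1 year

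*SAP*

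**What the plan says.** SAP version 3, Section 5, gives the safety and DFS windows as "Time from first study intervention to final assessment at 5 years" and the recurrence window as "Time from surgery to final assessment at 5 years". Protocol version 4, Section 3, Table 6 (repeated in the Synopsis), gives "Time from first study intervention to final assessment at 1 year" for safety and DFS and "Time from surgery to final assessment at 1 year" for recurrence.

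The rest of the SAP follows the protocol. Its modification history (Section 3) records for version 3.0 "Long-term Safety Follow-up period shortened to 1 year (previously 2 years) and removed Survival Follow-up". Section 6.4 schedules follow-up analyses "once all participants have completed the 1-year follow-up period and at the end of study". Section 7, which lists departures from the protocol's planned analyses, mentions no longer window.

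Follow-up beyond 1 year exists. Protocol Section 4.1.3 states "Participants who have already been followed up for more than 1 year (Long-term Safety or Survival Follow-up) will be discontinued" once the amendment is approved. The last cohort is named in the Synopsis: "the dose escalation in the Phase Ib part will be prematurely discontinued after completing the Cohort 5 of 150 mg".

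**The concern.** The endpoint table tells the programmer which events belong to an endpoint. Here it names a window that the trial no longer has. That would be a simple leftover if another SAP rule stopped counting at 1 year, but none does.

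Participants enrolled early were followed under a plan of 2 years plus survival follow-up. The last cohort stops at about Week 52. A late event in month 15 can therefore be counted for an early participant and could never be recorded for a late one. Cohorts opened one after another at different doses, so a crude percentage by dose level mixes dose with length of observation. The numbers are small: one extra event at a dose level with 3 to 6 participants (a planned cohort of 3, plus up to 3 more allowed by protocol Section 4.1.2) moves its percentage by 1/6 to 1/3, that is 17 to 33 points. Late radiotherapy toxicity is also the protocol's stated reason for keeping 1 year of follow-up.

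**Working it through.** There is no sample size, power or event count to reproduce, because the protocol (Section 9.1) plans no formal test. The check compares the documents and then works out time at risk.

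**1. Windows and stopping rules**

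| Analysis | SAP Section 5 | Protocol Table 6 | Stop at 1 year elsewhere in the SAP? |
|---|---|---|---|
| Late toxicities (15.2.3) | 5 years (safety row) | 1 year | No. They start after the on-treatment period and have no end |
| All deaths (15.3.1) | 5 years (safety row) | 1 year | No. Only the 60-day and the 30- and 90-day sub-counts are bounded |
| DFS (14.2) | 5 years | 1 year | No. Censored at the last usable tumor assessment |
| Recurrence (14.3) | 5 years | 1 year | No. Censored at the last assessment showing complete response, or at surgery if later |

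The cut-off rule in SAP Section 9 is one calendar date for everyone. It does not limit follow-up per participant.

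**2. What is exposed**

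- SAP Section 9 shows analyses by dose level and overall unless stated otherwise, so the late-toxicity table and the death count are crude counts by dose.
- DFS and recurrence Kaplan-Meier estimates are presented overall only (14.2.1, 14.3.1). Past 12 months they rest on the participants with longer follow-up.
- TEAE tables end 30 days after last treatment, and DLTs end with the DLT period. Neither changes.

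**3. Time at risk for late toxicity**

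Late time starts at treatment weeks × 7 + 30 days:
- 25 fractions: 5 × 7 + 30 = 65 days
- 28 fractions: 5.5 × 7 + 30 = 68.5 days

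With 1 year = 365.25 days, a participant stopped at 1 year has 365.25 − 65 = 300 late days (25 fractions) or 365.25 − 68.5 = 297 (28 fractions). Longer follow-up is an **assumption**, since the documents give no individual times:
- 1.5 years (547.9 days): 483/300 = 1.6 and 479/297 = 1.6
- 2 years (730.5 days): 665.5/300 = 2.2 and 662/297 = 2.2
- common 1-year cut: 1.0

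These are ratios of observation time, not of events. Protocol Section 8.3.1 stops recording unrelated AEs after short-term follow-up and unrelated SAEs at Week 27, so only treatment-related events can be added later. Event counts need not grow in proportion to time.

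**4. Dose or enrolment order**

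The Synopsis reports 19 participants treated at 50 to 250 mg by 06 May 2021, with the last cohort at 150 mg. The last dose lies inside the treated range. The documents do not say which cohorts passed 1 year.

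**5. The cut day**

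The Week 52 visit has a window of ± 2 weeks (protocol Table 2). The latest in-window visit is 54 × 7 = 378 days after first treatment. SAP Section 9 calls the first treatment day study day 1, so that visit falls on study day 379.

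**6. What a 1-year cut leaves unequal**

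The primary analysis (SAP 6.3) takes place when the last participant ends short-term follow-up, at about Week 19, or 133 days. That participant then has 133 − 65 = 68 late days (64.5 with 28 fractions), against 300 (297) for one with a full year. The ratio is 4.4 (4.6), with or without the cut.

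**The case against.** The 5-year cells are probably leftover text. Collection ends at 1 year under protocol version 4, the follow-up analysis is triggered at 1 year, and the wording alone creates no imbalance. That is fair: the imbalance comes from data already collected together with the missing cut. But the cells are current endpoint text, and they point a programmer away from cutting.

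A reader might go further and infer any of the following. The documents do not support them.

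- *Low doses look more toxic and 150 mg safer.* Doses up to 250 mg had been treated when 150 mg was named as the last cohort, so a higher-dose cohort may also have the longer follow-up. Only enrolment order is established.
- *Late-event risk is inflated about 2.2-fold.* That needs 2 years of actual follow-up and a constant rate of recordable events. The first is not documented. The second conflicts with the collection limits in protocol Section 8.3.1.
- *DFS and recurrence comparisons between doses are biased.* Both are pooled estimates with censoring, which allows for staggered follow-up. A thin tail outside the protocol window is the whole effect.

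Two practical objections stand. The cut cannot equalise follow-up at the primary analysis, where staggered follow-up comes with sequential escalation. It also takes late treatment-related events out of the main tables, and in a study of a radiosensitiser those must stay visible. Decision impact is limited too: the MTD and RP2D rest on DLTs, and Phase II will not be run.

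**Conclusion.** The point holds in a limited form. The contradiction is certain: 5 years against 1 year in three rows of current text, a difference of 4 years, with no SAP rule that limits counting to the protocol's window.

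The consequence is confined to the follow-up analyses. There the late-toxicity table and the total death count by dose level can include post-1-year events from earlier-enrolled participants only. This assumes that at least some such data are in the database, which protocol Section 4.1.3 makes likely but does not quantify. The effect on the counts, and its direction across doses, cannot be computed from the documents. The time-at-risk ratios of 1.6 to 2.2 are illustrations under assumed follow-up of 1.5 to 2 years. DLT and TEAE results do not change.

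It is worth correcting because the correction is cheap and the late-toxicity table is what the 1-year follow-up was kept for. It does not threaten the primary endpoint.

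**What to change.** 1. In SAP Section 5, change the three 5-year timeframes to 1 year after start of study intervention.
2. In SAP 15.2.3, 15.3.1, 14.2 and 14.3, state that tables and Kaplan-Meier estimates count events and follow-up only up to study day 379, with day 1 as the first treatment day, and that time-to-event data are censored administratively at that point. Use the same clock for recurrence. With surgery at Week 15 this leaves about 52 − 15 = 37 weeks from surgery to the Week 52 visit.
3. Show later events, including treatment-related SAEs, in listings flagged as after 1 year, and mention them in the report text. Collection and reporting under protocol Section 8.3.1 do not change.
4. State that at the primary analysis cut-off follow-up still differs between cohorts, so late-toxicity counts by dose should be read with that in mind.

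The cost is SAP wording, one date cut in the derivations and a listing flag. The downside is that post-1-year data leave the main tables.

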6.1 Analyses for SMC meetings

During Phase Ib, to decide on dose escalation, safety and PK analyses will be provided for the purpose of SMC meetings. The cut-off for dose escalation assessments by the SMC will usually be triggered by the completion of the DLT period (or dropout) of the last participant in the respective dose escalation cohort of usually 3 participants. In addition, once a participant completed the Short-term safety follow-up period at approximately 19 weeks after starting treatment, data of the participant will be reviewed. In the event of severe toxicity, an ad-hoc SMC meeting will be scheduled to decide on potential dose adjustment.

Details of analyses for SMC meetings will be specified in the appendix of this IAP.

6.2 Interim Analysis

After the last subject has finished the DLT period and after last subject has finished short term follow-up, an analysis on key safety and efficacy endpoints will be provided to decide on further development and potentially answer HA requests.

6.3 Primary Analysis

This analysis will be the main analysis of the safety and preliminary antitumor activity data from the dose escalation phase. The cut-off will be triggered by when the last participant enrolled in dose escalation reaches the end of the Short-term safety follow-up period or dies or prematurely discontinues the study for any reason, whichever occurs first.

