9.3 Populations for Analyses

The analysis populations are specified below ([Table 11](#)).

Table 11 Definition of Populations

Population	Description
Enrolled	All participants who sign informed consent.
DE	The DE Analysis Set will include all participants treated in dose escalation cohorts, who receive at least 80% of peposertib, 50% of capecitabine, and 80% of RT planned dose and complete the DLT period. The DE set will also include participants treated in dose escalation cohorts who experience a DLT during the DLT period regardless of the amount of each study intervention received/completion of the DLT period.
FAS/SAF	The FAS/SAF will include all participants who are enrolled in the study and received at least 1 dose of study intervention.
PK	The PK Analysis Set is defined as all participants who receive at least 1 dose of peposertib and have at least 1 quantifiable plasma concentration at a scheduled PK time point postdose.

cCR=Clinical Complete Response, DE=Dose Escalation, DLT=dose limiting toxicity, FAS=Full Analysis Set, PK=Pharmacokinetic, RT=radiotherapy, SAF=Safety.

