Analyses for the Bayesian dose escalation will be performed on the DE Analysis Set. Usually decisions on dose escalation are taken once all participants of the most recent cohort have completed the DLT period or dropped out. In exceptional cases, however, the SMC may decide on the next cohort earlier, i.e. before the last participant of a cohort has finished the DLT period (considering the model recommendation and risk of overdose). Per definition of the DLT analysis, participants who have not completed the DLT period are not included for update of the model, unless they experienced a DLT. However, such participants will be included at next SMC (if criteria for the DE Analysis Set are fulfilled).

Details on analyses for SMCs/CSR will be described in the corresponding SAP.

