9.4.4 Sequence of Analyses

The following analyses will be performed:

To decide on dose escalation, safety and PK analyses will be provided for the purpose of SMC meetings. The cut-off for dose escalation assessments by the SMC will usually be triggered by the completion of the DLT period (or dropout) of the last participant in the respective dose escalation cohort of usually 3 participants. In addition, once a participant completed the Short-term Safety Follow-up period at approximately 19 weeks after starting treatment, data of the participant will be reviewed. In the event of severe toxicity, an ad-hoc SMC meeting will be scheduled to decide on potential dose adjustment.

The cut-off for the primary analysis of the safety and preliminary antitumor activity data from the complete dose escalation will be triggered when the last participant enrolled in dose escalation reaches the end of the Short-term Safety Follow-up period or dies or prematurely discontinues the study for any reason, whichever occurs first.

Additional analyses might be performed, e.g. for publication purposes.

Follow-up analyses to report further efficacy and safety data will be done at the End of Study.

More details will be described in the Integrated Analysis Plan.

10 References

- Brookmeyer R and Crowley J. A confidence interval for the median survival time. *Biometrics*. 1982;38:29-41.
- Cockcroft DW and Gault MH. Prediction of creatinine clearance from serum creatinine. *Nephron*. 1976;16:31-41.
- Curtin NJ. DNA repair dysregulation from cancer driver to therapeutic target. *Nat Rev Cancer*. 2012;12:801-17.
- Ferrari L and Fichera A. Neoadjuvant chemoradiation therapy and pathological complete response in rectal cancer. *Gastroenterol Rep (Oxf)*. 2015;3(4):277-88.
- Furgason JM and Bahassi EM. Targeting DNA repair mechanisms in cancer. *Pharmacol Ther*. 2013;137:298-308.

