8.2 Definition of Analysis Populations and Subgroups

The analysis populations are specified below:

Table 1 Description of Analysis Sets

Population	Description
Enrolled	All participants who sign informed consent
Dose escalation (DE)	The DE Analysis Set will include all participants treated in dose escalation cohorts, who receive at least 80% of peposertib, 50% of capecitabine, and 80% of RT planned dose and complete the DLT period (5 or 5.5 weeks after start of treatment or for the entire duration of the treatment). The DE set will also include participants treated in dose escalation cohorts who experience a DLT during the DLT period regardless of the amount of each study intervention received/completion of the DLT period.
Full analysis set (FAS)	The FAS will include all participants who are enrolled in the study and received at least 1 dose of study intervention.
Safety (SAF)	The SAF analysis set will include all participants who receive at least 1 dose of study intervention. Participants will be analyzed according to the actual treatment they receive. In case of different doses received the dose with high number of administrations will be used as actual treatment.
Pharmacokinetics (PK)	The PK analysis set is defined as all participants who receive at least 1 dose of peposertib and have sufficient peposertib plasma concentration data to enable the calculation of at least 1 PK parameter. Sufficient concentration data is defined as at least 3 valid, post dose, concentration points in the PK profile to obtain any PK parameter.

DE=dose escalation, DLT=dose limiting toxicity, FAS=full analysis set, PK=pharmacokinetic, RT=radiotherapy, SAF=safety

Table 2 Summary of Analyses and associated Analysis Set

Analyses	ENR	SAF	FAS	DE	PK
Disposition	✓				
Baseline assessments		✓			
Past and concomitant therapies		✓			
Compliance and exposure		✓			
Primary endpoint: DLTs				✓	
Efficacy			✓		
Safety and tolerability		✓			
CCI					
Pharmacokinetics					✓
CCI					

DE=dose escalation, ENR=enrolled, FAS=full analysis set, PK=pharmacokinetic, SAF=safety

9 General Specifications for Data Analyses

Study intervention groups

Unless otherwise indicated all analyses will be presented separately for each dose level, and overall.

Data handling after cut-off date

Data after cut-off do not undergo the cleaning process, will not be included in SDTMs, and will not be displayed in any listings or used for statistical analyses or imputation.

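### The main-analysis cut-off depends on the last-enrolled participant alone, so an early death or withdrawal of that person could cut up to about two cohort-mates before surgery

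*SAP*

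**What the plan says.** SAP 6.3 describes the main analysis of safety and preliminary antitumor activity. Its data cut-off is tied to one person: "last participant enrolled in dose escalation reaches the end of the Short-term safety follow-up period or dies or prematurely discontinues the study". The earliest of these events counts, and the cause of a discontinuation makes no difference. Protocol 9.4.4 matches it: the cut-off falls "when the last participant enrolled in dose escalation reaches the end of the Short-term Safety Follow-up period or dies or prematurely discontinues the study". Neither section mentions the status of the other participants.

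Three other rules determine what the cut-off does:

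- **Later data.** SAP Section 9 states: "Data after cut-off do not undergo the cleaning process, will not be included in SDTMs". They are also kept out of listings, analyses and imputation.
- **Missing responses.** Efficacy uses the FAS, meaning everyone enrolled and dosed. Under SAP 14.1 and its Table 5, a participant who has had no surgery is a pCR non-responder. One with neither surgery nor the cCR procedures is a non-responder for the composite. One with cCR and no surgery is a composite responder. SAP 14.4.1 sets NAR to missing if any component is missing.
- **Other triggers.** For dose-escalation decisions, protocol 9.4.2 normally waits "once all participants of the most recent cohort have completed the DLT period or dropped out". SAP 6.4 waits for all participants to complete 1 year.

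**The concern.** One person's exit date fixes the data for everyone. A participant still on study, dosed and awaiting restaging or surgery has no category of their own. Under the FAS rules, a response not yet assessed looks the same as no response.

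At stake are the items measured from Week 14 onwards: cCR, pCR, the pCR/cCR composite, NAR, and the perioperative adverse events collected at Week 19. The people exposed are those who started last, so the effect would fall on a single cohort. SAP Section 9 presents results by dose level, where one or two participants weigh heavily.

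**Working it through.** **Timeline.** SAP 6.1 places the end of short-term follow-up "approximately 19 weeks after starting treatment". The stated periods reproduce this: 5.5 weeks of treatment + 13.5 weeks of follow-up = 19.0 weeks, or 5 + 14 = 19 weeks. Protocol 4.1.3 says "Surgical intervention must be performed 15 weeks" (± 14 days) after the start of study intervention. 15 − 5.5 = 9.5 weeks after radiotherapy, as that section states.

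**When a cohort-mate is cut.** Let the last-enrolled participant leave the study at week *t* of their own clock, and let a cohort-mate have started *s* weeks earlier. At the cut-off the cohort-mate is at week *t* + *s*. They are cut before surgery if *t* + *s* < 15, that is *s* < 15 − *t*. With the surgery window, 15 becomes 13 to 17.

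| Exit week *t* | Start gap *s* must be below (surgery at Week 15) | With surgery at Week 13 / Week 17 |
|---|---|---|
| 5 | 10 weeks | 8 / 12 |
| 5.5 | 9.5 weeks | 7.5 / 11.5 |
| 9 | 6 weeks | 4 / 8 |
| 12 | 3 weeks | 1 / 5 |
| 14 | 1 week | none / 3 |

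The documents do not give start gaps within the last cohort. I considered gaps of 0 to 12 weeks.

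**Which exit weeks remain possible.** Protocol version 4.0 says that all participants have completed treatment, so *t* is at least about 5. Protocol 1.1 counts 19 treated by 06 May 2021, and SAP version 3 was approved on 07–08 July 2021, 62 to 63 days later (8.9 to 9.0 weeks). If the last participant had started by 06 May and was still on study at approval, *t* is at least about 9 and the gap must be under about 6 weeks.

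**How a cut participant is classified.**

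| Cohort-mate's position at cut-off | pCR | cCR | pCR/cCR | NAR |
|---|---|---|---|---|
| Before Week 14 assessment | non-responder | non-responder | non-responder | missing |
| After Week 14, cCR, before planned surgery | non-responder | responder | responder | missing |
| After Week 14, no cCR, before surgery | non-responder | non-responder | non-responder | missing |
| After surgery, before Week 19 | as observed | as observed | as observed | available if staged |

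In every row the Week 19 safety visit is absent. The composite can err in either direction: a future responder may be counted as a failure, and a Week 14 cCR that surgery would have overturned may be counted as a success.

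**Size.** Of the 19 treated, 16 had finished Week 19 by 06 May 2021 (protocol 1.1), leaving 19 − 16 = 3. Excluding the trigger person, at most 2 are exposed.

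- Largest shift in an overall response rate: 2/19 = 10.5 percentage points.
- Illustration: 4/19 = 21.1% (Clopper-Pearson 95% CI 6.1 to 45.6) would be reported as 2/19 = 10.5% (1.3 to 33.1).
- Within a three-person cohort: up to 2/3.
- Expected downward shift if both are cut before Week 14, at assumed response rates *p* of 10% to 30%: 2*p*/19 = 1.1 to 3.2 points.

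**The case against.** The strongest reply is that the wording is shorthand. Protocol 9.4.4 and SAP 6.1 describe the dose-escalation cut-off as completion or dropout of the last participant in the cohort, while protocol 9.4.2 gives the same rule as all participants having completed or dropped out. On that reading, SAP 6.3 also means that everyone has finished. This is plausible, but SAP 6.3 identifies the person by order of enrolment and attaches death and discontinuation to that person. A programmer applying it as written would cut on that date.

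The limits on the consequence carry more weight, and they stand:

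- **The event is uncommon.** It needs death or withdrawal from the study. Protocol 7.1 keeps participants who stop study intervention under follow-up, so stopping treatment alone does not fire the trigger.
- **The DLT endpoint over the DLT period is not affected.** Protocol 6.6.1 ends that period with chemoradiotherapy, which everyone had completed.
- **The data are deferred, not lost.** SAP 6.4 reports further efficacy and safety after 1 year. SAP 6.2 also plans an analysis after the last subject finishes short-term follow-up, without a death or dropout alternative. It covers key endpoints only and does not change the 6.3 cut-off.

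A reader might infer more than the documents support. Protocol 4.1.2 allows up to three parallel participants, which suggests a larger exposed group, but only three people in total were unfinished. The Enrolled set is defined by signed consent ("All participants who sign informed consent"), which suggests that a screen failure could set the cut-off. The trigger, however, speaks of enrolment in dose escalation and of reaching the end of follow-up, and screening is closed.

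**Conclusion.** The point holds as a minor one. The rule as written lets one participant's early death or study withdrawal set the cut-off while others are still awaiting restaging or surgery, and the SAP's missing-data rules would then classify those others from incomplete data.

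The exposure is at most about two participants: 10.5 percentage points on an overall rate and up to two of three in the last cohort, in either direction for the composite. This assumes that nobody was enrolled after 06 May 2021 and that none of the three unfinished participants had already left. If someone was enrolled later, the planned cohort size still implies a last cohort of about three. If the last-enrolled participant completes follow-up normally, this early-exit problem does not arise. A reader might conclude that the antitumor results are generally unreliable; the documents do not support that.

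**What to change.** In SAP 6.3, define the cut-off as the date by which *every participant given at least one dose of study intervention in dose escalation has completed the Short-term Safety Follow-up period, died, or left the study prematurely*. Make the same change in protocol 9.4.4 at any next amendment. The point does not justify an amendment of its own, since Appendix 2 requires ethics approval for each one.

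The cost is one sentence per document and a contingent delay. If the last-enrolled participant leaves at week *t* and a cohort-mate started the same day, the cut-off moves by 19 − *t* weeks: 14 weeks for an exit at Week 5 and 10 weeks for an exit at Week 9. Any earlier start by the cohort-mate shortens this. With the change, no participant still on study can be cut before surgery and the Week 19 visit.
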